7.3.2 Secondary Analysis

The secondary purpose of the study is to determine the persistent antimicrobial activity of the two Investigational Products, Active Control and Negative Control by calculating the responder rate along with 95% lower confidence bound at 6-hour post-treatment time point for each body site using an Exact method (one-sided). The goal is to demonstrate a success proportion $\geq 95\%$ on both the abdomen and the inguen with 95% confidence. However, since this is a Phase II study to inform design of future efficacy studies and is not designed to provide statistically powered evidence of efficacy, the lower confidence bounds cannot lie entirely above 95%.

An example of comparing responder rates to 95% for each treatment is provided below.

Table 7: Example: Analysis results for responder rate for Groin

Treatment	Time Point	N Non-responder	N Responder	N Total	Responder Rate	95% Lower Confidence Bound
A	6 Hours	1	35	36	97.2%	87.5%
B	6 Hours	0	36	36	100.0%	92.0%
C	6 Hours	2	34	36	94.4%	83.5%
D	6 Hours	1	35	36	97.2%	87.5%

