## 2.0 OBJECTIVE

The primary objective of this study is to compare the immediate antimicrobial properties of octenidine dihydrochloride [OCT] in isopropyl alcohol - clear in a single-use applicator and octenidine dihydrochloride [OCT] in isopropyl alcohol - tinted in a single-use applicator to a Negative Control and an FDA NDA-approved Active Control. Single use applicators filled with 0.9% saline will serve as the Negative Control and Chloraprep® – Hi-Lite Orange® applicator will serve as the Active Control. In agreement with the Food and Drug Administration Tentative Final Monograph (TFM) for *Effectiveness Testing of a Patient Preoperative Skin Preparation*, a log10 reduction study will be used to determine antimicrobial efficacy based on the statistical analyses outlined in published letters from the FDA on January 19, 2017. The updated analysis applies a non-inferiority requirement of the investigative product to an FDA NDA-approved control with a 0.5 log10 margin and a 1.2 log10 superiority requirement over a Negative Control. The average treatment effect of the investigative products compared to the Active and the Negative Controls will be determined from a linear regression of post-treatment log10 bacterial counts after correcting for pre-treatment log10 bacterial loads. The secondary objective is to determine the persistent antimicrobial activity of the two Investigative Products, Active Control, and the Negative Control. Log10 bacterial counts at 6 hours for each treatment site will be converted to a binary (yes or no) success measure with success defined as having skin flora counts that are less than or equal to the baseline skin flora counts. The objective is to demonstrate a success proportion  $\geq 95\%$  on both the abdomen and the inguen with 95% confidence.

Testing will be performed according to the procedures outlined in the Food and Drug Administration Tentative Final Monograph (TFM) for *Effectiveness Testing of a Patient Preoperative Skin Preparation* (FR 59:116, 17 June 94, pp. 31450-31452). The test methods for this evaluation will be based on ASTM Standard Test Method E1173-15,

*Evaluation of Preoperative, Precatheterization, or Preinjection Skin Preparations and the test criteria from the deferral letters published by the FDA on January 19, 2017.*

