## 7.0 SCOPE

The objective of this study is to compare the immediate and persistent antimicrobial properties of octenidine dihydrochloride [OCT] in isopropyl alcohol - clear in a single-use applicator and octenidine dihydrochloride [OCT] in isopropyl alcohol - tinted in a single-use applicator to a Negative Control, 0.9% saline applied with a single use applicator, and an FDA-approved Active Control, ChloraPrep® – Hi-Lite Orange® applicator. Testing will be performed according to the procedures outlined in the Food and Drug Administration Tentative Final Monograph (TFM) for *Effectiveness Testing of a Patient Preoperative Skin Preparation* (FR 59:116, 17 June 94, pp. 31450-31452). The test methods for this evaluation will be based on ASTM E1173-15, *Standard Test Method for Evaluation of Preoperative, Precatheterization, or Preinjection Skin Preparations* and the test criteria from the deferral letters from the FDA published on January 19, 2017.

A sufficient number of male and female, overtly healthy, volunteer subjects at least 18 years of age, will be enrolled in the screening phase to ensure that the total numbers of evaluable samples collected from inguinal and abdominal regions meet or exceed 36 evaluable test sites per test material (total minimum of 144 each for inguinal and abdominal regions). Subjects must satisfy all Screening Day and Treatment Day Inclusion/Exclusion Criteria prior to screening sample collection and Treatment Day procedures. If the required numbers of subjects do not qualify from the initial screening group, additional volunteers will be recruited.

Following a 14-day restriction period, subjects with resident bacterial flora that meet the specified criteria will be eligible to proceed to the treatment phase of testing. Specific baseline criteria for subjects will be  $\geq 3.00 \log_{10}$  CFU/cm^2 from the skin of the abdomen and  $\geq 5.00 \log_{10}$  CFU/cm^2 from the skin of the inguen. Evaluations will consist of samples collected at baseline, 30 seconds  $\pm$  5 seconds, 10 minutes  $\pm$  30 seconds, and at 6 hours  $\pm$  30 minutes post-treatment. All plating for this study will be conducted in duplicate using the pour-plating technique and incubated at  $30 \pm 2$  °C for 72 hours  $\pm$  4 hours. The left and right abdominal test sites will be 5"  $\times$  5" areas of skin.

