6.2 Analysis Population Set(s)

For each treatment per body site, the number of subjects randomized, the number of subjects available for mITT analysis [average treatment effect (ATE), responder rate and product expression volumes] and / or for per-protocol analysis [average treatment effect (ATE), responder rate and product expression volumes] at each post-treatment time point (30 seconds, 10 minutes and 6 hours) will be provided in tables below (cf. Table 2, Table 3 and Table 4). If the number of subjects randomized is different from the number of subjects randomized with treatments received, the number of subjects randomized with treatment received will be also summarized.

Table 2: Number of subjects randomized

Treatment	Body Site	N Subjects Randomized with Treatment Received
A	Abdomen	
B	Abdomen	
C	Abdomen	
D	Abdomen	
A	Groin	
B	Groin	
C	Groin	
D	Groin	

Table 3: Number of subjects available for mITT analysis

Treatment	Body Site	N Subjects for mITT ATE at 30 sec	N Subjects for mITT ATE at 10 min	N Subjects for mITT ATE at 6 hr	N Subjects for mITT Responder Rate at 6 hr	N Subjects for mITT Product Expression Volumes
A	Abdomen					
B	Abdomen					
C	Abdomen					
D	Abdomen					
A	Groin					
B	Groin					
C	Groin					
D	Groin					

Table 4: Number of subjects available for per-protocol analysis

Treatment	Body Site	N Subjects for Per-Protocol ATE at 30 sec	N Subjects for Per-Protocol ATE at 10 min	N Subjects for Per-Protocol ATE at 6 hr	N Subjects for Per-Protocol Responder Rate at 6 hr	N Subjects for Per-Protocol Product Expression Volumes
A	Abdomen					
B	Abdomen					
C	Abdomen					
D	Abdomen					
A	Groin					
B	Groin					
C	Groin					
D	Groin					

7 Statistical Analysis/Calculations

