7.3.1 Primary Analysis

The primary purpose of the study is to compare the immediate antimicrobial activity of the Investigational Products to the Negative Control and Active Control according to the methods described in the FDA TFM with the statistical analyses outlined in a deferral letter published January 19, 2017. There are two test criteria that drive the hypotheses.

- Evaluate the average treatment effect (ATE) of the Active Control (AC) compared to each Investigational Product (IP) at 30 seconds and 10 minutes for non-inferiority on both abdomen and groin. ATE of the AC compared to either IP is defined as the contrast of the treatment effect of the IP minus the treatment effect of the AC (IP - AC) in the linear regression. Statistical hypotheses are:
 - Ho: The upper bound 95% confidence interval of the ATE of IP - AC $\geq 0.5 \log_{10}$
 - Ha: The upper bound 95% confidence interval of the ATE of IP - AC $< 0.5 \log_{10}$
- Evaluate the Average Treatment effect (ATE) of each Investigational Product (IP) compared to the Negative Control (NC) at 30 seconds and 10 minutes on both abdomen and inguen anatomical area. ATE of the IP compared to the NC is defined as the contrast of the treatment effect of the NC minus the treatment effect of the IP (NC - IP) in the linear regression. Statistical hypotheses are:
 - Ho: The lower bound 95% confidence interval of the ATE of NC - IP $\leq 1.2 \log_{10}$
 - Ha: The lower bound 95% confidence interval of the ATE of NC - IP $> 1.2 \log_{10}$

Ho is the null hypothesis and Ha is the alternative hypothesis.

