7.3.3.2 Log Reduction

\log_{10} reductions will be compared between test materials by an Analysis of Variance (ANOVA) for each body site based on mITT data and/or per-protocol data. In the ANOVA model, the response is the \log_{10} reduction and the predictors are treatment and time point as well as the interaction between treatment and time point. The average difference in log reduction between treatments per time point will be estimated. However, all conclusions for the difference in the average treatment effect between treatments will be based on the primary analysis only.

An example for results of comparisons above can be found in Tables 10.

Table 10: Example: results for product comparisons within time interval (10 minutes) for Groin

Comparison	N Pairs	Difference	Conf Int	Conclusion
IP1 Baseline-A 10 min vs. AC Baseline-AC 10 min	36	0.13	-0.44, 0.70	no sign. diff.
IP2 Baseline-A 10 min vs. AC Baseline-AC 10 min	36	0.11	-0.65, 0.87	no sign. diff.
IP1 Baseline-A 10 min vs. VC Baseline-VC 10 min	36	0.33	-0.44, 1.09	no sign. diff.
IP2 Baseline-A 10 min vs. VC Baseline-AC 10 min	36	0.33	-0.44, 1.09	no sign. diff.

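### Persistence is stated as a comparison with both controls, but no 6-hour comparison between arms that can carry a conclusion is specified

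*SAP*

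**What the plan says.** **The aim.** Protocol 7.0 sets out to "compare the immediate and persistent antimicrobial properties of octenidine dihydrochloride" in both formulations, and names the comparators: "to a Negative Control, 0.9% saline applied with a single use applicator, and an FDA-approved Active Control". Protocol 7.4 and SAP 4 likewise describe the persistent effect as relative to both controls. Protocol 2.0 is weaker: "The secondary objective is to determine the persistent antimicrobial activity of the two Investigative Products, Active Control, and the Negative Control". Protocol 7.2 and 15.2 and SAP 3.2 follow that weaker wording.

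**The 6-hour decision analysis.** SAP 7.3.2 specifies "calculating the responder rate along with 95% lower confidence bound at 6-hour post-treatment time point for each body site". A site is a responder if its 6-hour count is no higher than its own Treatment Day baseline. Each arm's rate and lower bound are set against 95%.

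**The between-arm contrasts.** SAP 7.3.1 evaluates each product against the Active Control "at 30 seconds and 10 minutes for non-inferiority on both abdomen and groin", and against the Negative Control at the same two times.

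**The exploratory model.** Protocol 7.3 and 15.3 and SAP 7.3.3.2 fit an ANOVA of log10 reduction on treatment, time point and their interaction. It estimates treatment differences per time point, but "all conclusions for the difference in the average treatment effect between treatments will be based on the primary analysis only". Protocol 15.3 lists three post-treatment times for the descriptive statistics and then refers to 'both' times for the comparison.

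**The counts.** SAP Table 3 has a column headed "N Subjects for mITT ATE at 6 hr", and Table 4 has the per-protocol equivalent.

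**The concern.** The plan states a comparative question about persistence, collects the data to answer it in four randomised arms, and then specifies no analysis from which the answer may be drawn.

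This matters because own-baseline success is not specific to the product. Three things other than the antiseptic can affect it:

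- **Scrubbing.** Every material, saline included, is scrubbed on for 30 seconds (abdomen) or 2 minutes (inguen), according to Appendix 1.
- **Dressing.** The 6-hour sampling site is covered with a sterile dressing after the 10-minute sample (Protocol 13.6). The documents do not say in which direction this would move counts.
- **Selection.** A site enters the mITT set only if its Treatment Day baseline reaches 3.00 (abdomen) or 5.00 log10 (inguen). The same reading is then the success reference, so regression to the mean favours success.

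These factors are common to all arms, and a between-arm contrast largely removes them. If saline also scored high, the plan would offer no estimate or interval of the difference from which to say so. The study's purpose is to inform later efficacy trials, and that estimate is what those trials would need.

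**Working it through.** **1. Which analyses reach 6 hours, and what each can support**

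| Analysis | Between arms? | Covers 6 h? | May support a conclusion? |
|---|---|---|---|
| Primary regression (SAP 7.3.1) | Yes | No: 30 s and 10 min | Yes |
| Responder rate (SAP 7.3.2, Protocol 15.2) | No: each arm against 95% | Yes | Yes |
| Treatment-by-time ANOVA (SAP 7.3.3.2, Protocol 7.3, 15.3) | Yes | Can, but Protocol 15.3 is unclear | No |
| Average treatment effect at 6 h (SAP Tables 3 and 4) | Counted only | Counted only | Not specified |

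No row has Yes in all three columns.

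**2. Reproducing the plan's figures.** SAP Table 7 is an example with n = 36. The one-sided exact lower bound is the 5% quantile of Beta(x, n − x + 1):

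- 34/36: 83.5%
- 35/36: 87.5%
- 36/36: 0.05^(1/36) = 92.0%

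All three match Table 7. Each bound uses one arm's counts only, so the method has no between-arm element. With zero failures, a lower bound of 95% needs 0.05^(1/n) ≥ 0.95, so n ≥ 59.

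**3. How far own-baseline success could be moved without a product effect.** The documents give no variance components, so these inputs are assumptions:

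- Site mean ~ N(μ, τ), with μ = 5.0 or 5.5 (inguen), 2.7 or 3.2 (abdomen), and τ = 0.5 or 0.7.
- Independent reading error with SD 0.25 or 0.40.
- A site is kept if its screening reading is at or above the limit and its Treatment Day baseline is within the mITT range (3.00 to 5.50 abdomen, 5.00 to 7.50 inguen).
- Success means the 6-hour reading is at or below the baseline reading.
- There were 1,000,000 draws per setting.

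| Lasting non-product loss at 6 h (log10) | Responders, range over settings |
|---|---|
| 0 | 52% to 64% |
| 0.3 | 74% to 87% |
| 0.5 | 85% to 96% |
| 1.0 | 97% to 100% |

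Selection alone therefore adds about 2 to 14 points to the 50% expected from two exchangeable readings. Approaching 95% takes roughly 0.5 to 1.0 log10 of loss still present at 6 hours.

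**4. What an added 6-hour contrast would give.** Take 36 sites per arm, treated as independent, and the SDs of log10 reduction in the illustrative Table 9 (0.89 to 1.18). The 95% half-width is 1.96 × SD × √(2/36):

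- SD 0.89: 1.96 × 0.210 = 0.41 log10
- SD 1.18: 1.96 × 0.278 = 0.55 log10

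Contrasting responder rates instead would be less informative when saline scores high. With a product rate of 97% assumed and two-sided 5%, power (pooled z / exact Fisher) is 89% / 86% against saline at 70%, 62% / 48% at 80%, and 22% / 6% at 90%. The saline rates are assumed too. This favours the regression on log10 counts.

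**The case against.** The strongest reply has five parts.

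- **The named secondary objective only says 'determine'.** That is so, and the responder analysis delivers it. The mismatch is between Protocol 7.0 and 7.4 with SAP 4 on one side, and Protocol 2.0, 7.2 and 15.2 with SAP 3.2 on the other. Rewording the first group would remove the inconsistency, but would leave the comparative question unanswered with the data in hand.
- **Protocol 1.0 defines persistence against own baseline.** This stands. It is a reason to keep the responder rate, and a reason not to add a new success rule, for which the documents give no source.
- **The ANOVA and the side-by-side tables already show the comparison.** A reader might infer that 6-hour persistence cannot be attributed to the product at all. The documents do not support that: saline is randomised, concurrent and reported at 6 hours, and the ANOVA can estimate the difference. The gap is in what may be concluded, not in the data.
- **No arm can pass the formal goal.** At n = 36 the best possible bound is 92.0%, and SAP 7.3.2 itself says the bounds cannot clear 95%. So no false claim can pass at the stated confidence; only point estimates could mislead.
- **The harm depends on an assumed loss.** This also stands. A reader might infer that an inert product would look persistent. With no effect, at most 64% of sites respond, and the chance of 35/36 or better is about 2 in a million. At 0.3 log10 loss it is at most about 4%. SAP Table 7, where arm D equals arm A at 35/36, is a placeholder and says nothing about saline.

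**Conclusion.** The point holds as a gap in the prespecified inference. Three places in the documents make persistence relative to the controls, and no analysis that may support a conclusion compares arms at 6 hours. Two loose ends add to it: the word 'both' in Protocol 15.3, and the 6-hour treatment-effect counts in SAP Tables 3 and 4 that no section uses. Those counts may mean that a 6-hour contrast was intended, but the documents do not settle this.

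The responder rate alone does not isolate the product effect. By how much is unknown: the 52% to 64% and the 0.5 to 1.0 log10 rest on assumed SDs, site means and a constant loss, and the documents give no estimate of the mechanical effect of saline scrubbing at 6 hours.

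This is a worthwhile, low-cost improvement to an unpowered Phase II study, not a flaw that invalidates it.

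**What to change.** In SAP 7.3.2 and Protocol 15.2:

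1. Keep the responder rate as planned.
2. Add, per body site, the regression of 6-hour log10 count on treatment and baseline log10 count. Report NC − IP1, NC − IP2, IP1 − AC and IP2 − AC with 95% CIs as secondary estimates.
3. Allow for two treatments per subject, for example with a random subject effect, as SAP 7.3.3.3 already does for product expression.
4. State that persistence relative to the controls may be described from these estimates, and adjust the restriction on conclusions in SAP 7.3.3.2 and Protocol 7.3 and 15.3 to match.
5. Correct 'both' in Protocol 15.3 so that 6 hours is included. The 6-hour columns in SAP Tables 3 and 4 then have a use.

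Do not add a pass/fail attribution rule.

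The cost is wording in two documents and one more run of an existing model, extended for the pairing, on data already collected. There are no new subjects or samples. The downside is one more set of secondary results, which could make a statement about persistence less favourable.

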7.3.3 Exploratory Analyses

7.3.3.1 Summary Statistics

Summary statistics will be provided for \log_{10} CFU/cm² of skin, \log_{10} CFU/cm² reduction and product expression volumes based on mITT data and/or per-protocol data. For continuous variables, data will be summarized with the following descriptive statistics: number of observations, mean (LSMean), median, standard deviation and range (minimum - maximum). See examples for summary statistics Tables 8 and 9 below for \log_{10} CFU/cm² and \log_{10} CFU/cm² reduction.

Table 8: Example: summary statistics for \log_{10} CFU/cm² for Groin

\log_{10} CFU/cm ²	Treatment	Time Point	N	Mean	LSMean	Median	SD	Range
\log_{10} CFU/cm ²	A	Baseline	36	5.92	5.92	5.82	0.53	5.01 - 7.23
\log_{10} CFU/cm ²	A	30 Seconds	36	3.29	3.29	3.44	1.10	0.89 - 5.89
\log_{10} CFU/cm ²	A	10 Minutes	36	3.05	3.05	3.09	0.72	1.22 - 4.09
\log_{10} CFU/cm ²	A	6 Hours	36	5.78	5.78	5.66	0.54	5.05 - 7.04
\log_{10} CFU/cm ²	B	Baseline	36	3.27	3.27	3.43	1.09	0.00 - 4.95
\log_{10} CFU/cm ²	B	30 Seconds	36	3.26	3.26	3.39	0.89	0.00 - 4.47
\log_{10} CFU/cm ²	B	10 Minutes	36	5.92	5.92	5.82	0.53	5.01 - 7.23
\log_{10} CFU/cm ²	B	6 Hours	36	3.27	3.27	3.43	1.09	0.00 - 4.95
\log_{10} CFU/cm ²	C	Baseline	36	3.26	3.26	3.39	0.89	0.00 - 4.47
\log_{10} CFU/cm ²	C	30 Seconds	36	3.05	3.05	3.09	0.72	1.22 - 4.09
\log_{10} CFU/cm ²	C	10 Minutes	36	3.29	3.29	3.44	1.10	0.89 - 5.89
\log_{10} CFU/cm ²	C	6 Hours	36	3.05	3.05	3.09	0.72	1.22 - 4.09
\log_{10} CFU/cm ²	D	Baseline	36	5.78	5.78	5.66	0.54	5.05 - 7.04
\log_{10} CFU/cm ²	D	30 Seconds	36	3.27	3.27	3.43	1.09	0.00 - 4.95
\log_{10} CFU/cm ²	D	10 Minutes	36	5.92	5.92	5.82	0.53	5.01 - 7.23
\log_{10} CFU/cm ²	D	6 Hours	36	3.29	3.29	3.44	1.10	0.89 - 5.89

Table 9: Example: summary statistics for \log_{10} CFU/cm² reduction for Groin

\log_{10} CFU/cm ² reduction	Treatment	N	Mean	LSMean	Median	SD	Range
\log_{10} CFU/cm ² reduction	A Baseline - 30 Seconds	36	2.63	2.63	2.57	1.18	0.20 - 4.80
\log_{10} CFU/cm ² reduction	A Baseline - 10 Minutes	36	2.83	2.83	2.83	0.89	1.24 - 4.86
\log_{10} CFU/cm ² reduction	A Baseline - 6 Hours	36	2.52	2.52	2.33	1.09	0.83 - 5.50
\log_{10} CFU/cm ² reduction	B Baseline - 30 Seconds	36	2.53	2.53	2.30	1.11	0.90 - 5.50
\log_{10} CFU/cm ² reduction	B Baseline - 10 Minutes	36	2.63	2.63	2.57	1.18	0.20 - 4.80
\log_{10} CFU/cm ² reduction	B Baseline - 6 Hours	36	2.53	2.53	2.30	1.11	0.90 - 5.50
\log_{10} CFU/cm ² reduction	C Baseline - 30 Seconds	36	2.83	2.83	2.83	0.89	1.24 - 4.86
\log_{10} CFU/cm ² reduction	C Baseline - 10 Minutes	36	2.52	2.52	2.33	1.09	0.83 - 5.50
\log_{10} CFU/cm ² reduction	C Baseline - 6 Hours	36	2.63	2.63	2.57	1.18	0.20 - 4.80
\log_{10} CFU/cm ² reduction	D Baseline - 30 Seconds	36	2.52	2.52	2.33	1.09	0.83 - 5.50
\log_{10} CFU/cm ² reduction	D Baseline - 10 Minutes	36	2.83	2.83	2.83	0.89	1.24 - 4.86
\log_{10} CFU/cm ² reduction	D Baseline - 6 Hours	36	2.53	2.53	2.30	1.11	0.90 - 5.50

7.3.3.2 Log Reduction

\log_{10} reductions will be compared between test materials by an Analysis of Variance (ANOVA) for each body site based on mITT data and/or per-protocol data. In the ANOVA model, the response is the \log_{10} reduction and the predictors are treatment and time point as well as the interaction between treatment and time point. The average difference in log reduction between treatments per time point will be estimated. However, all conclusions for the difference in the average treatment effect between treatments will be based on the primary analysis only.

An example for results of comparisons above can be found in Tables 10.

Table 10: Example: results for product comparisons within time interval (10 minutes) for Groin

Comparison	N Pairs	Difference	Conf Int	Conclusion
IP1 Baseline-A 10 min vs. AC Baseline-AC 10 min	36	0.13	-0.44, 0.70	no sign. diff.
IP2 Baseline-A 10 min vs. AC Baseline-AC 10 min	36	0.11	-0.65, 0.87	no sign. diff.
IP1 Baseline-A 10 min vs. VC Baseline-VC 10 min	36	0.33	-0.44, 1.09	no sign. diff.
IP2 Baseline-A 10 min vs. VC Baseline-AC 10 min	36	0.33	-0.44, 1.09	no sign. diff.

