3.4 Endpoints

- Primary Endpoints
 - Log CFU/cm² of skin for each treatment per body site per time point.
- Secondary Endpoints
 - Responder rates will be calculated by converting each log₁₀ CFU/cm² reduction at 6 hours post-treatment time point to a binary (yes or no) success measure. Success at 6 hours post-treatment time point is defined as having skin flora counts that are less than or equal to the baseline skin flora counts on both body sites.
- Exploratory Endpoints
 - Log₁₀ CFU/cm² reductions from baseline for each treatment per body site per post-application time point.
 - Product expression volumes: the weight of the treatment applied to a test site will be estimated by subtracting the weight measurement (g) of the treatment after the application from the weight of the treatment (g) before application.
- Safety Endpoints
 - Skin irritation scores (Erythema, Edema, Rash and Dryness scores for each time point)

4 Sample Size

A sufficient number of volunteers will be enrolled in the screening phase such that the total numbers of evaluable samples collected from groin and abdominal regions are not less than 36 evaluable test sites from each treatment arm (minimum of 144 each for groin and abdominal regions). A minimum of 72 evaluable subjects is required to achieve a total of at least 144 test sites for groin and abdominal regions. Subjects must satisfy all Screening Day and Treatment Day Inclusion/Exclusion Criteria prior to screening sample collection and Treatment Day procedures. If the required numbers of subjects do not qualify from the initial screening group, additional volunteers will be recruited.

This is a Phase II study to assess the immediate and persistent antimicrobial effect of the Investigational Products relative to the Negative Control and the Active Control using a log₁₀ reduction study (i.e., average treatment effect) according to the procedures outlined in the Food and Drug Administration Tentative Final Monograph (TFM) for Effectiveness Testing of a Patient Preoperative Skin Preparation (FR 59:116, 17 June 94, pp. 31450-31452) and the test criteria outlined in the deferral letters from the FDA published on January 19, 2017. The purpose is to inform design of future efficacy studies, therefore no sample size calculation was performed to provide statistically-powered evidence of efficacy as part of this study. The sample size is deemed adequate for these purposes.

5 Intended Statistical Software

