7.3 Analysis Methods

For each body site, when per-protocol data are different from mITT data for average treatment effect (ATE), responder rate, log reduction or product expression volumes, per-protocol analysis and mITT analysis will be performed separately using the same statistical methods. The following analysis methods will be applied to both per-protocol analysis and mITT analysis, both abdomen and groin.

An alpha level of 5% (two-sided) is used for all analyses.

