A linear regression model for each body site will be used for primary analysis. In the model, the response is the post-treatment \log_{10} bacterial counts and predictors are the treatment effect as a fixed effect and the pre-treatment \log_{10} bacterial counts as a covariate. The interaction between the treatment and pre-treatment \log_{10} bacterial counts will be also explored. If there is no significant interaction detected between treatment and pre-treatment \log_{10} bacterial counts, the interaction term will be removed from the model and the average difference between treatments will be estimated from the linear regression model after correcting for pre-treatment \log_{10} bacterial counts. If there is a significant interaction detected between treatment and pre-treatment \log_{10} bacterial counts, the average difference between treatments will be estimated from the linear regression model at the average of the covariate. Additional factors (e.g., technician and subject demographics) may be also included in the model and the effects will be investigated.

Since the study will declare success when and only when both non-inferiority and superiority are demonstrated for both abdomen and groin, no multiplicity adjustment for multiple primary objectives is required.

An example for results of comparisons above can be found in Tables 5 and 6. All results that do not meet the targets are highlighted.

Table 5: Example: ATE for IP1/IP2 - AC for Groin

Comparison	Time Point	N Pairs	Difference in ATE	Conf Int	Meet Non-inferiority Criteria
IP1 - AC	30 Seconds	36	-0.50	-1.31, 0.30	Yes
IP2 - AC	30 Seconds	36	-0.35	-1.00, 0.31	Yes
IP1 - AC	10 Minutes	36	0.32	-0.52, 1.15	No
IP2 - AC	10 Minutes	36	0.50	-0.39, 1.39	No

Table 6: Example: ATE for NC - IP1/IP2 for Groin

Comparison	Time Point	N Pairs	Difference in ATE	Conf Int	Meet Superiority Criteria
NC - IP1	30 Seconds	36	1.35	1.01, 1.59	No
NC - IP2	30 Seconds	36	1.23	0.90, 1.50	No
NC - IP1	10 Minutes	36	0.4	0.02, 0.82	No
NC - IP2	10 Minutes	36	1.6	1.28, 1.91	Yes

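### The exploratory log-reduction ANOVA leaves out the Treatment Day baseline count, and the analysis text specifies no baseline-adjusted between-arm contrast at 6 hours

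*SAP*

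**What the plan says.** SAP 7.3.3.2 compares the arms, per body site, with an ANOVA whose response is the log10 "reduction and the predictors are treatment and time point as well as the interaction between treatment and time point". Its output is a contrast at each time: "The average difference in log reduction between treatments per time point will be estimated". Protocol 7.3 and 15.3 give the same model. None of the three places includes a baseline term.

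The primary model in SAP 7.3.1 handles baseline differently. Its response is the post-treatment log10 "bacterial counts and predictors are the treatment effect as a fixed effect and the pre-treatment" log10 count as a covariate. Its hypotheses cover two times only; for the Active Control the comparison is "compared to each Investigational Product (IP) at 30 seconds and 10 minutes for non-inferiority on both abdomen and groin", and the Negative Control comparison uses the same two times.

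At 6 hours the secondary analysis in SAP 7.3.2 proceeds "by calculating the responder rate along with 95% lower confidence bound at 6-hour post-treatment time point for each body site". That is a one-sample summary for each arm. Log reduction is nevertheless an exploratory endpoint at every sampling time (SAP 3.4: "reductions from baseline for each treatment per body site per post-application time point"), so 6 hours falls within the ANOVA.

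The SAP also limits the weight of this analysis: "However, all conclusions for the difference in the average treatment effect between treatments will be based on the primary analysis only".

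**The concern.** A reduction is the baseline count minus the post-treatment count. Comparing reductions without a baseline covariate assumes that each extra log10 at baseline adds exactly one log10 after treatment. If the true slope is below 1, an arm that happens to start higher shows a larger reduction with no extra product effect. Part of the error in the single baseline reading also enters every reduction unnecessarily.

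A slope below 1 is plausible here. Each test site is divided into four areas, each sampled once (Protocol 13.3), so the baseline and post-treatment readings come from different patches of skin. Counts below 1 CFU/cm² are set to 1 (Protocol 13.10), which flattens the relation wherever a product drives counts to that floor.

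Example Table 10 attaches an interval and a significance conclusion to each comparison, and SAP 7.3 sets the level: "An alpha level of 5% (two-sided) is used for all analyses". At 30 seconds and 10 minutes a call in that table could differ from the primary result partly because baseline is treated differently. At 6 hours the analysis text describes no adjusted result to set beside it. The study is meant to inform later efficacy studies, so a less noisy 6-hour difference would be useful.

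**Working it through.** **1. Sites per arm.** There are 6 treatment pairs with 12 subjects each (SAP 3.3): 6 × 12 = 72 subjects. Each treatment is in 3 pairs: 3 × 12 = 36 sites per arm and region, and 4 × 36 = 144 sites. The plan's figures reproduce. The documents give no power or precision figure for this ANOVA.

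**2. Formulas** (one time point, sites treated as independent, same SDs in both arms). Let SDb, SDp and SDr be the SDs of the baseline, the post-treatment count and the reduction, r the baseline/post correlation and b the slope.
- Covariance = (SDb² + SDp² − SDr²)/2; r = covariance/(SDb × SDp); b = covariance/SDb²
- Var(reduction) = SDb² + SDp² − 2 r SDb SDp
- Var(adjusted) = SDp² (1 − r²)
- The two variances differ by SDb² (1 − b)², so nothing is lost only when b = 1.
- Share of a baseline imbalance carried into the unadjusted difference = 1 − b

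**3. Can the SAP's example tables size the gain?** Groin values from Tables 8 and 9:
- Arm A, 30 seconds (SDs 0.53, 1.10, 1.18): covariance 0.0493, r = 0.085, b = 0.175. Variance 1.392 falls to 1.201, a cut of 13.7%. Means agree: 5.92 − 3.29 = 2.63.
- Arm A, 10 minutes (0.53, 0.72, 0.89): r = 0.009, b = 0.013, cut 34.6%. Means do not agree: 5.92 − 3.05 = 2.87, but the table shows 2.83.
- Arm A, 6 hours (0.53, 0.54, 1.09): covariance −0.308, r = −1.08, which is impossible. Means: 5.92 − 5.78 = 0.14, but the table shows 2.52.
- Arm D, 30 seconds (0.54, 1.09, 1.09): r = 0.25, b = 0.50, cut 6%.
- Arms B and C have example groin baselines of 3.27 and 3.26, below the 5.00 floor for the mITT set.

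These are table shells, not data. They do not size the gain, least of all at 6 hours.

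**4. Assumed range.** Take SDb = 0.53, SDp = 0.72 or 1.10, and r from 0.1 to 0.5. The standard error of a baseline difference between two arms is 0.53 × √(2/36) = 0.125. A chance imbalance of 1.96 standard errors is therefore 0.245 log10. The last column is 0.245 × (1 − b).

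| r | SDp | b | Var(reduction) | Var(adjusted) | Cut | Shift, log10 |
|---|---|---|---|---|---|---|
| 0.1 | 0.72 | 0.136 | 0.7230 | 0.5132 | 29% | 0.21 |
| 0.1 | 1.10 | 0.208 | 1.3743 | 1.1979 | 13% | 0.19 |
| 0.3 | 0.72 | 0.408 | 0.5703 | 0.4717 | 17% | 0.15 |
| 0.3 | 1.10 | 0.623 | 1.1411 | 1.1011 | 4% | 0.09 |
| 0.5 | 0.72 | 0.679 | 0.4177 | 0.3888 | 7% | 0.08 |
| 0.5 | 1.10 | 1.038 | 0.9079 | 0.9075 | 0% | −0.01 |

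**5. Bias or noise?** The 72-subject paired layout was simulated 4,000 times per setting (slope 0.175, residual SD 1.096, left/right baseline correlation 0, 0.5 and 0.8). With no true effect, both estimators averaged about 0. The unadjusted difference correlated 0.34 to 0.36 with the chance baseline imbalance; the adjusted one correlated about 0. Their standard errors were about 0.275 and 0.258.

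**6. Does other text supply the adjustment?** The baseline ANOVA in Protocol 15.1 tests balance but triggers no change of model. The optional baseline-effect analyses in Protocol 7.3 and 15.3 vary the baseline limits and add no covariate here. SAP Tables 3 and 4 have columns for an ATE at 6 hours, but SAP 7.3.1 states no contrast at that time. Protocol 15.3 lists three sampling times and then refers to two.

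**The case against.** The strongest reply is that the plan has already settled which result counts. Conclusions on treatment differences belong to the primary regression, which adjusts for baseline, so a conflicting call in Table 10 has a stated tie-break. Change from baseline is a legitimate pre-specified exploratory endpoint, and the 6-hour objective is a responder proportion per arm, not a difference between arms. All of this stands, and it confines the point to an exploratory refinement.

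A reader might infer more in three ways, none of which the documents support:
- That the ANOVA is biased. Randomisation makes its difference correct on average; the issue is chance imbalance and precision.
- That the plan contains no other 6-hour comparison. The 6-hour ATE columns in SAP Tables 3 and 4 suggest that a baseline-adjusted contrast may be intended. It is unspecified, and Protocol 15.3 leaves it unclear whether the ANOVA comparison itself covers 6 hours.
- That the example SDs give a definite gain in interval width or power. The tables contradict themselves. The ANOVA pools its residual over arms and time points, whereas the calculation here uses a single time point. Power for a 0.5 log10 difference answers no question in the plan: 0.5 is the non-inferiority margin, and the study is explicitly unpowered.

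**Conclusion.** The omission is real, is the same in both documents, and is not repaired elsewhere. It is minor. It does not touch the primary conclusions at 30 seconds and 10 minutes. What remains is a 6-hour between-arm difference that is either unadjusted or, if a 6-hour ATE is intended, not specified.

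The size at 6 hours is unknown. Under the assumed SDs and correlations the variance cut runs from about 29% to 0%, and it vanishes as the slope approaches 1. The range rests on independent sites, equal SDs across arms and a single time point.

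**What to change.** Either of two changes closes the gap:
- In SAP 7.3.3.2, add the Treatment Day baseline log10 count and its interaction with time point to the log-reduction model, and report adjusted differences per time point at the mean baseline. With baseline in the model, the treatment differences have the same size whether the response is the reduction or the post-treatment count. State whether the treatment-by-baseline interaction explored in the primary model is also examined here.
- Or state in the SAP that the primary baseline-adjusted regression is also run at 6 hours as exploratory. This would give the 6-hour ATE columns in Tables 3 and 4 a defined analysis.

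In both cases keep the raw mean reductions in Table 9 as descriptive statistics, and make clear which sampling times the between-arm comparison covers.

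The cost is small: no new data, a few degrees of freedom and short SAP wording. If Protocol 7.3 and 15.3 are aligned as well, Protocol 16.2 requires a written amendment to the review board. The first option also yields results at 30 seconds and 10 minutes that largely repeat the primary analysis.
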